6.1.4 PREPARATION

IBRUTINIB

N/A

PEMBROLIZUMAB

The investigator shall take responsibility for and shall take all steps to maintain appropriate records and ensure appropriate supply, storage, handling, distribution and usage of investigational product in accordance with the protocol and any applicable laws and regulations.

Clinical Supplies will be provided by Merck as summarized in the table below:

Table Product descriptions

Product Name & Potency	Dosage Form
Pembrolizumab 100 mg/ 4mL	Solution for Injection

Pembrolizumab is provided as a liquid solution (100 mg/vial) in Type I glass vials intended for single use only.

The liquid drug product are a clear to opalescent solutions, essentially free of visible particles. The liquid product is intended for IV administration. The liquid drug product can be further diluted with normal saline or 5% dextrose in the concentration range of 1 to 10 mg/mL in intravenous (IV) containers made of polyvinyl chloride (PVC) or non-PVC material. Reconstituted vials should be immediately used to prepare the infusion solution in the IV bag and the infusion solution should be immediately administered. Diluted pembrolizumab solutions may be stored at room temperature for a cumulative time of up to 4 hours. This includes room temperature storage of admixture solutions in the IV bags and the duration of infusion. In addition, IV bags can be stored at 2 to 8°C for up to a cumulative time of 20 hours. This recommendation is based on up to 24 hours of room temperature and up to 24 hours of refrigerated stability data of diluted pembrolizumab solutions in the IV bags.

6.1.5 DOSING AND ADMINISTRATION

IBRUTINIB

Ibrutinib will be administered orally once daily at approximately the same time each day at the dose of 420

mg daily (3 capsules of 140 mg daily). Capsules will be swallowed whole with water. Capsules shall not be opened, broken or chew.

PEMBROLIZUMAB

Pembrolizumab will be administered intravenously at 200 mg every 3 weeks

6.1.6 ROUTE OF ADMINISTRATION

IBRUTINIB

Ibrutinib is only indicated for oral administration

PEMBROLIZUMAB

Pembrolizumab will be administered as is approved route of administration (IV)

6.1.7 STARTING DOSE AND DOSE ESCALATION SCHEDULE

IBRUTINIB

The starting dose will be the recommended for chronic lymphocytic leukemia at 420 mg daily (three capsules daily orally). There will be no escalation schedule of ibrutinib in this study.

PEMBROLIZUMAB

The starting dose of pembrolizumab will be at the recommended of 200 mg IV every 3 weeks. There will be no dose escalation of pembrolizumab in this study.

6.1.8 DOSE ADJUSTMENTS/MODIFICATIONS/DELAYS

GENERAL MANAGEMENT OF DOSE ADJUSTMENT S/MODIFICATIONS WITH IBRUTINIB AND/OR PEMBROLIZUMAB

Below is the table for general management/adjustments of ibrutinib and pembrolizumab for hematologic and non-hematologic adverse events.

If study treatment is held for an adverse event and the subject is approved to resume treatment, the subject will resume with the timepoint at which the treatment was held.

Toxicity	Grade	Dose Modification	Toxicity Management	Agent to be considered for dose modification
Thrombocytopenia (Unless it is related to CLL bone marrow involvement)	1,2 3 (Platelets < 50 000 cells/mm ³ [50×10^9])	N/A Ibrutinib: No dose modification required Pembrolizumab: No dose modification required	N/A Monitor CBC/differential at least weekly Platelet transfusions are permitted per AABB guidelines	Ibrutinib Pembrolizumab

Ibrutinib and PD-1 Blockade to Improve Immune Dysfunction in
Chronic Lymphocytic Leukemia
Protocol <#>

	4 (Platelets < 25 000 cells/mm ³ [50×10^9])	
Ibrutinib: If thrombocytopenia resolves to \leq Grade 1 (platelets $\geq 75,000$ cells /mm³ [75×10^9/L] or baseline, restart the dose. If toxicity recurs, reduce dose by 140 mg. If toxicity persists following two dose reductions, discontinue ibrutinib
 
Pembrolizumab: Decision to discontinue will depend upon clinical situation and per clinical investigator's judgment and in consultation with Supporting company
	Monitor CBC/differential at least weekly Platelet transfusions are permitted per AABB guidelines	
Neutropenia (Unless it is related to CLL bone marrow involvement)	1,2	N/A	N/A	Ibrutinib Pembrolizumab
	3 ANC < 1000 cells/m ³ [1×10^9])	
Ibrutinib Hold ibrutinib if Grade 3 associated with infection or fever (temperature $\geq 38.5^{\circ}\text{C}$) If neutropenia resolves to \leq Grade 1 (ANC ≥ 1500 /mm³ [$\geq 1.5 \times 10^9$ /L]) or baseline, restart the dose. If toxicity recurs, reduce dose by 140 mg. If toxicity persists following 2 dose reductions, discontinue the drug
 
Pembrolizumab Hold pembrolizumab until resolution to \leq Grade 1 or baseline For AEs that downgrade to \leq Grade 2 within 7 days or resolve to \leq Grade 1 or baseline within 14 days, resume IP/study regimen administration at next scheduled dose. Otherwise, discontinue pembrolizumab
	Monitor CBC/differential at least weekly Use of myeloid growth factors (MGF) are permitted per ASCO or NCCN guidelines	
	4 ANC < 500 cells/m ³ [1×10^9])	
Ibrutinib Hold ibrutinib for Grade 4 If neutropenia resolves to \leq Grade 1 (ANC ≥ 1500 /mm³ [$\geq 1.5 \times 10^9$ /L]) or baseline, restart the dose. If toxicity recurs, reduce dose by 140 mg. If toxicity persists following 2 dose reductions, discontinue the drug
 
Pembrolizumab Decision to discontinue will depend upon clinical situation and per clinical investigator's judgment and in consultation with supporting company
	Monitor CBC/differential at least weekly Use of myeloid growth factors (MGF) are permitted per ASCO or NCCN guidelines	
Non-Hematological	1	N/A		Pembrolizumab

toxicity (non-immune related toxicity)	2	Pembrolizumab Hold drug until resolution to Grade \leq 1 toxicity or baseline Ibrutinib No dose interruption is needed		Ibrutinib
	3 or 4	Pembrolizumab Hold drug until resolution to Grade \leq 1 toxicity or baseline For AEs that downgrade to \leq Grade 2 within 7 days or resolve to \leq Grade 1 or baseline within 14 days, resume IP/study regimen administration at next scheduled dose. Otherwise, discontinue pembrolizumab For Grade 4 AEs the decision to discontinue will depend upon clinical situation and per clinical investigator's judgment and in consultation with supporting company Ibrutinib Hold Ibrutinib If toxicity resolves to \leq Grade 1 or baseline, restart the dose. If toxicity recurs, reduce dose by 140 mg. If toxicity persists following two dose reductions, discontinue ibrutinib		

IBRUTINIB DOSE MODIFICATIONS

Interrupt ibrutinib therapy for any Grade 3 or greater non-hematological toxicities, Grade 3 or greater neutropenia with infection or fever, or Grade 4 hematological toxicities. Once the symptoms of the toxicity have resolved to Grade 1 or baseline (recovery), ibrutinib therapy may be reinitiated at the starting dose. If the toxicity reoccurs, reduce dose by one capsule (140 mg per day). A second reduction of dose by 140 mg may be considered as needed. If these toxicities persist or recur following two dose reductions, discontinue ibrutinib.

Recommended dose modifications are described below:

Toxicity occurrence	Withhold/Discontinue ibrutinib?
First	Restart at 420 mg daily
Second	Restart at 280 mg daily
Third	Restart at 140 mg daily
Forth	Discontinue ibrutinib

MANAGEMENT/SUPPORTIVE CARE OF IMMUNE RELATED ADVERSE EVENTS RELATED TO PEMBROLIZUMAB

Events of clinical interest of a potential immunologic etiology (irECIs) may be defined as an adverse event of unknown etiology, associated with drug exposure and is consistent with an immune phenomenon. irAEs may be predicted based on the nature of the pembrolizumab compound, its mechanism of action, and reported experience with immunotherapies that have a similar mechanism of action. Special attention should be paid to AEs that may be suggestive of potential irAEs. An irAE can occur shortly after the first dose or several months after the last dose of treatment.

If an irAE is suspected, efforts should be made to rule out neoplastic, infectious, metabolic, toxin or other etiologic causes prior to labeling an adverse event as an irAE. Information on how to identify and evaluate irAEs has been developed and is included in the Event of Clinical Interest and Immune-Related Adverse Event Guidance Document located in the Administrative Binder. Subjects who develop a Grade 2 or higher irAE should be discussed immediately with the Sponsor.

It is not expected that ibrutinib will cause immune related AEs.

Recommendations to managing irAEs not detailed elsewhere in the protocol are detailed in the table below

irAE	Withhold/Discontinue pembrolizumab?	Supportive Care
Grade 1	No action	Provide symptomatic treatment
Grade 2	May withhold pembrolizumab	Consider systemic corticosteroids in addition to appropriate symptomatic treatment
Grade 3 and Grade 4	Withhold pembrolizumab Discontinue if unable to reduce corticosteroid dose to < 10 mg per day prednisone equivalent within 12 weeks of toxicity	Systemic corticosteroids are indicated in addition to appropriate symptomatic treatment. May utilize 1 to 2 mg/kg prednisone or equivalent per day. Steroid taper should be considered once symptoms improve to Grade 1 or less and tapered over at least 4 weeks.

Management of specific irAEs

Pneumonitis:

For Grade 2 events, treat with systemic corticosteroids. When symptoms improve to Grade 1 or less, steroid taper should be started and continued over no less than 4 weeks.

For Grade 3-4 events, immediately treat with intravenous steroids. Administer additional anti-inflammatory measures, as needed.

Add prophylactic antibiotics for opportunistic infections in the case of prolonged steroid administration.

Diarrhea/Colitis:

Subjects should be carefully monitored for signs and symptoms of enterocolitis (such as diarrhea, abdominal pain, blood or mucus in stool, with or without fever) and of bowel perforation (such as peritoneal signs and ileus).

All subjects who experience diarrhea/colitis should be advised to drink liberal quantities of clear fluids. If sufficient oral fluid intake is not feasible, fluid and electrolytes should be substituted via IV infusion. For Grade 2 or higher diarrhea, consider GI consultation and endoscopy to confirm or rule out colitis.

For Grade 2 diarrhea/colitis, administer oral corticosteroids.

For Grade 3 or 4 diarrhea/colitis, treat with intravenous steroids followed by high dose oral steroids.

When symptoms improve to Grade 1 or less, steroid taper should be started and continued over no less than 4 weeks

Type 1 diabetes mellitus

If new onset, including diabetic ketoacidosis [DKA]) or \geq Grade 3 Hyperglycemia, if associated with ketosis (ketonuria) or metabolic acidosis (DKA)

For T1DM or Grade 3-4 Hyperglycemia

Insulin replacement therapy is recommended for Type I diabetes mellitus and for Grade 3-4 hyperglycemia associated with metabolic acidosis or ketonuria.

Evaluate patients with serum glucose and a metabolic panel, urine ketones, glycosylated hemoglobin, and C-peptide.

Hypophysitis:

For Grade 2 events, treat with corticosteroids. When symptoms improve to Grade 1 or less, steroid taper should be started and continued over no less than 4 weeks. Replacement of appropriate hormones may be required as the steroid dose is tapered.

For Grade 3-4 events, treat with an initial dose of IV corticosteroids followed by oral corticosteroids. When symptoms improve to Grade 1 or less, steroid taper should be started and continued over no less than 4 weeks. Replacement of appropriate hormones may be required as the steroid dose is tapered.

Hyperthyroidism or Hypothyroidism:

Thyroid disorders can occur at any time during treatment. Monitor patients for changes in thyroid function (at the start of treatment, periodically during treatment, and as indicated based on clinical evaluation) and for clinical signs and symptoms of thyroid disorders.

Grade 2 hyperthyroidism events (and Grade 2-4 hypothyroidism):

In hyperthyroidism, non-selective beta-blockers (e.g. propranolol) are suggested as initial therapy.

In hypothyroidism, thyroid hormone replacement therapy, with levothyroxine or liothyroinine, is indicated per standard of care.

Grade 3-4 hyperthyroidism

Treat with an initial dose of IV corticosteroid followed by oral corticosteroids. When symptoms improve to Grade 1 or less, steroid taper should be started and continued over no less than 4 weeks. Replacement of appropriate hormones may be required as the steroid dose is tapered.

Hepatic:

For Grade 2 events, monitor liver function tests more frequently until returned to baseline values (consider weekly).

Treat with IV or oral corticosteroids

For Grade 3-4 events, treat with intravenous corticosteroids for 24 to 48 hours.

When symptoms improve to Grade 1 or less, a steroid taper should be started and continued over no less than 4 weeks

Renal Failure or Nephritis:

For Grade 2 events, treat with corticosteroids.

For Grade 3-4 events, treat with systemic corticosteroids.

When symptoms improve to Grade 1 or less, steroid taper should be started and continued over no less than 4 weeks.

Management of Pembrolizumab Infusion Related Reactions (IRR):

Signs and symptoms usually develop during or shortly after drug infusion and generally resolve completely within 24 hours of completion of infusion. Management of IRR are recommended based on Moffitt institutional policies. Below is a table of general recommendations.

NCI CTCAE Grade	Treatment	Premedication at subsequent dosing
Grade 1 Mild reaction; infusion interruption not indicated; intervention not indicated	Increase monitoring of vital signs as medically indicated until the subject is deemed medically stable in the opinion of the investigator.	None
Grade 2 Requires infusion interruption but responds promptly to symptomatic treatment (e.g., antihistamines, NSAIDS,	Stop Infusion and monitor symptoms. Additional appropriate medical therapy may include but is not limited to: IV fluids	Subject may be premedicated 1.5h (\pm 30 minutes) prior to infusion of pembrolizumab with:

NCI CTCAE Grade	Treatment	Premedication at subsequent dosing
narcotics, IV fluids); prophylactic medications indicated for <=24 hrs	
Antihistamines NSAIDS Acetaminophen Narcotics
 
Increase monitoring of vital signs as medically indicated until the subject is deemed medically stable in the opinion of the investigator.
 
If symptoms resolve within one hour of stopping drug infusion, the infusion may be restarted at 50% of the original infusion rate (e.g. from 100 mL/hr to 50 mL/hr). Otherwise dosing will be held until symptoms resolve and the subject should be premedicated for the next scheduled dose.
 
Subjects who develop Grade 2 toxicity despite adequate premedication should be permanently discontinued from further trial treatment administration.
	
Diphenhydramine 50 mg po (or equivalent dose of antihistamine).
 
Acetaminophen 500-1000 mg po (or equivalent dose of antipyretic).

Grades 3 or 4 Grade 3: Prolonged (i.e., not rapidly responsive to symptomatic medication and/or brief interruption of infusion); recurrence of symptoms following initial improvement; hospitalization indicated for other clinical sequelae (e.g., renal impairment, pulmonary infiltrates) Grade 4: Life-threatening; pressor or ventilatory support indicated	
Stop Infusion.
 
Additional appropriate medical therapy may include but is not limited to:
 
IV fluids Antihistamines NSAIDS Acetaminophen Narcotics Oxygen Pressors Corticosteroids Epinephrine
 
Increase monitoring of vital signs as medically indicated until the subject is deemed medically stable in the opinion of the investigator.
 
Hospitalization may be indicated.
 
Subject is permanently discontinued from further trial treatment administration.
	No subsequent dosing

Appropriate resuscitation equipment should be available in the room and a physician readily available during the period of drug administration.
 
For Further information, please refer to the Common Terminology Criteria for Adverse Events v5.0 (CTCAE) at http://ctep.cancer.gov
		

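### In the 6.1.8 dose table, the Grade 4 platelet and ANC thresholds carry the Grade 3 figures in 10^9 units, so the two grades share one cut-off although they call for different actions

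*Combined protocol and SAP*

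**What the plan says.** The table in section 6.1.8 sets the actions for low counts by grade.

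- **Platelets, Grade 3:** count below 50 000/mm^3, bracket 50 × 10^9. For ibrutinib: "Ibrutinib: No dose modification required". Pembrolizumab is likewise unmodified.
- **Platelets, Grade 4:** "Platelets < 25 000 cells/mm"^3, bracket again 50 × 10^9. The ibrutinib entry opens at recovery, "Ibrutinib: If thrombocytopenia resolves to" Grade 1 or baseline, and goes on to restart, reduction and discontinuation. Stopping pembrolizumab is left to the investigator in consultation with the supporting company.
- **ANC, Grade 3:** count below 1000, bracket 1 × 10^9. For ibrutinib: "Hold ibrutinib if Grade 3 associated with infection or fever". For pembrolizumab: "Hold pembrolizumab until resolution to" Grade 1 or baseline, with discontinuation if recovery misses the stated time limits.
- **ANC, Grade 4:** "ANC < 500 cells/m" (the quotation stops before the exponent), bracket again 1 × 10^9. For ibrutinib: "Hold ibrutinib for Grade 4". For pembrolizumab: "Decision to discontinue will depend upon clinical situation" and investigator judgment.

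The ibrutinib paragraph below the table requires interruption for Grade 4 hematological toxicities. The step-down table after it restarts a first occurrence at 420 mg. Section 8.2.1 grades all adverse events by CTCAE v5.0.

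**The concern.** A threshold printed in two units should describe one cut-off. In both Grade 4 rows it describes two, and the bracketed one is the cut-off of the row above. Anyone reading the table in 10^9/L finds Grades 3 and 4 starting at the same value, with nothing in those units to separate them.

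The separation matters because the rows differ in action. For platelets, Grade 3 leaves both drugs alone, while Grade 4 calls for ibrutinib to be interrupted. For an ANC without infection or fever, Grade 3 leaves ibrutinib running and holds pembrolizumab, while Grade 4 holds ibrutinib and leaves pembrolizumab discontinuation to judgment.

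The missing hold adds to this. The Grade 4 platelet cell directly follows a Grade 3 row that requires no modification, and it begins with how to restart. Section 2.3.1 reports bleeding of Grade 3 or higher in 3% of ibrutinib patients, some of it fatal, so this hold is better stated than implied.

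**Working it through.** **Inputs.** Seven count and bracket pairs printed in the thrombocytopenia and neutropenia rows of the 6.1.8 table. The ANC counts are taken as per mm^3, the unit printed in the restart rules of the same rows.

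**Step 1: conversion.** Count per mm^3 × 10^6 = count per litre; divide by 10^9 to compare with the bracket.

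| Threshold | Count | Converted (10^9/L) | Bracket (10^9) | Bracket ÷ converted |
|---|---|---|---|---|
| Platelets, Grade 3 | 50 000 | 50 | 50 | 1.0 |
| Platelets, Grade 4 | 25 000 | 25 | 50 | 2.0 |
| Platelets, restart | 75 000 | 75 | 75 | 1.0 |
| ANC, Grade 3 | 1000 | 1.0 | 1 | 1.0 |
| ANC, restart (Grade 3 row) | 1500 | 1.5 | 1.5 | 1.0 |
| ANC, Grade 4 | 500 | 0.5 | 1 | 2.0 |
| ANC, restart (Grade 4 row) | 1500 | 1.5 | 1.5 | 1.0 |

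Five of seven pairs agree. The two that fail are the Grade 4 thresholds. Each is off by a factor of 2, and each equals the Grade 3 bracket. That pattern points to copying from the row above, not to a different threshold having been chosen.

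**Step 2: what the shared cut-off does.** The ranges that the counts place in Grade 3 only, but the brackets place in both grades, are:

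- Platelets 25 to 50 × 10^9/L. For example, 40 × 10^9/L is 40 000/mm^3. By count it is Grade 3 and ibrutinib continues. By bracket it satisfies both rows: no modification, and the Grade 4 interruption.
- ANC 0.5 to 1.0 × 10^9/L without infection or fever. By count it is Grade 3: ibrutinib continues and pembrolizumab is held. By bracket it also satisfies the Grade 4 row: ibrutinib is held, and pembrolizumab discontinuation is left to judgment.

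Values below 25 and below 0.5 satisfy both brackets too, but they also satisfy both printed counts, and the higher grade is the evident reading there.

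**Step 3: the hold.** Four ibrutinib cells in the table carry a restart rule: Grade 4 platelets, Grade 3 ANC with infection or fever, Grade 4 ANC, and Grade 3 or 4 non-hematological toxicity. Three state a hold first. The Grade 4 platelet cell does not.

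**Step 4: how often the rows might be consulted.** Section 2.3.1 gives Grade 3 or 4 rates on single-agent ibrutinib of 24% for neutropenia and 8% for thrombocytopenia. If those rates applied to 25 patients, which is an assumption, 25 × 0.24 = 6 and 25 × 0.08 = 2 patients would reach these rows. This is expected use of the rows, not a rate of misdosing.

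**The case against.** The strongest reply is that the right answer is available several times over. The row label, the printed counts and CTCAE v5.0 all identify the grade. The ibrutinib paragraph supplies the hold, and an instruction to restart presupposes a stop. The eligibility table in section 5.1 states ANC and platelets per mcL, section 7.7 gives the WBC limit as an absolute count, and nothing in the protocol says that the single site's laboratory reports in 10^9/L. All of that stands. It limits the practical weight of the point, but does not make the brackets correct.

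Three stronger readings are tempting, and the documents do not support them.

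- A reader might infer that the bracket sends platelets of 40 × 10^9/L to Grade 4. It does not select Grade 4. The same bracket stands in the Grade 3 row, so the result is two matching rows, and a visible duplicate may well send the reader back to the count.
- A reader might infer that the error drives a patient down to 280 mg or 140 mg. The step-down table restarts a first occurrence at 420 mg, so a single misreading costs only a temporary ibrutinib interruption. Lower doses require repeated occurrences.
- A reader might take the Grade 4 platelet cell as a second, conflicting rule under which ibrutinib continues. The paragraph in the same section rules that out; the cell is incomplete, not contradictory.

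**Conclusion.** The point holds as an error in the dosing table. Two of seven bracketed thresholds, both Grade 4, are twice the correct figure and repeat the Grade 3 value, so in 10^9/L the table cannot distinguish grades that carry different instructions. The absent hold in the Grade 4 platelet cell is a lesser defect, because the section supplies it elsewhere.

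The conclusion rests on treating the printed counts as the intended thresholds. The five agreeing pairs, and the fact that only the counts separate the two grades, support this. How often anyone would work from the bracket cannot be derived from the documents, so no misdosing probability is claimed. For ibrutinib, a Grade 4 reading of a Grade 3 count errs towards an unneeded hold. For pembrolizumab with a low ANC, it replaces a stated hold with a cell about discontinuation, which does not itself say to keep dosing. Nothing here touches sample size, power, error rates or endpoints. It should be corrected, because staff should not have to reconcile two cut-offs when dosing a patient.

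**What to change.** In the 6.1.8 table:

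1. Change the Grade 4 platelet bracket to 25 × 10^9/L.
2. Change the Grade 4 ANC bracket to 0.5 × 10^9/L.
3. Begin the ibrutinib entry for Grade 4 thrombocytopenia with an instruction to hold ibrutinib, matching the Grade 4 neutropenia cell and the ibrutinib paragraph.

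The cost is text in three cells, plus the IRB review that section 13.2 requires for any amendment; it can travel with the next one. There are no added visits, tests or patients, and dosing policy does not change.

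### Section 6.1.8 prints two thresholds, a factor of two apart, in each haematological Grade 4 row, and writes a pembrolizumab hold for Grade 3 neutropenia but none for Grade 4

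*Combined protocol and SAP*

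**What the plan says.** Section 6.1.8 gives one table for both drugs, by toxicity and grade.

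- **Thrombocytopenia, Grade 3:** "Platelets < 50 000 cells/mm"³, bracket 50 × 10⁹. Neither drug is modified.
- **Thrombocytopenia, Grade 4:** "Platelets < 25 000 cells/mm"³, bracket again 50 × 10⁹. Ibrutinib has a restart-and-reduce rule after recovery. Stopping pembrolizumab is left to judgment.
- **Neutropenia, Grade 3:** "ANC < 1000 cells/m"³, bracket 1 × 10⁹. Ibrutinib is held only with infection or fever. For pembrolizumab the entry opens "Hold pembrolizumab until resolution to" Grade 1 or less, or baseline. It then lets dosing resume at the next scheduled dose if the event falls to Grade 2 or less within 7 days, or reaches Grade 1 or baseline within 14 days, and ends "Otherwise, discontinue pembrolizumab".
- **Neutropenia, Grade 4:** "ANC < 500 cells/m"³, bracket again 1 × 10⁹. For ibrutinib: "Hold ibrutinib for Grade 4". For pembrolizumab, the whole entry is "Decision to discontinue will depend upon clinical situation and per clinical investigator's judgment and in consultation with supporting company".
- **Non-haematological, Grade 3 or 4:** one cell holds pembrolizumab, gives the same 7/14-day rule, and adds the Grade 4 discretion sentence.

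The paragraph under the table interrupts ibrutinib for Grade 4 haematological toxicity and does not mention pembrolizumab. The later instruction in 6.1.8 to withhold pembrolizumab at Grades 3 and 4 belongs to the table for immune-related events. Section 8.2.1 grades all adverse events by CTCAE 5.0.

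**The concern.** The table tells the treating physician when to interrupt, resume or stop each drug. It does this partly with its own printed counts, and it does not say whether those counts or the CTCAE grade govern if the two differ.

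In both haematological Grade 4 rows the count and the bracket cannot both be the threshold. A patient whose count lies between them meets the Grade 3 row by one figure and the Grade 4 row by the other, and the two rows instruct differently. Section 5.3 makes all faculty of the Lymphoma Section sub-investigators, so the same blood count could be handled in two ways, each defensible from the text.

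The pembrolizumab column raises a second question. The less severe neutropenia row has a hold, a recovery criterion and a time limit. The more severe row has none of these in writing. Within the Grade 3 entry, the opening hold and the 7-day clause do not clearly agree on when dosing may resume.

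**Working it through.** **Step 1. Convert every threshold pair.** One mm³ is 10⁻⁶ L, so a count per mm³ divided by 1,000 is the value in 10⁹/L. The inputs are the six pairs printed in the platelet and neutrophil rows of section 6.1.8. Two readings are assumed. The neutrophil thresholds are printed per m³ and are read as per mm³, the unit of the recovery threshold in the same rows. The threshold brackets carry no volume unit and are read as per litre, as in the recovery brackets.

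| Pair | Printed count per mm³ | Count ÷ 1,000 | Printed bracket (10⁹) | Bracket ÷ converted count |
|---|---|---|---|---|
| Platelets, Grade 3 | 50,000 | 50 | 50 | 1.0 |
| Platelets, Grade 4 | 25,000 | 25 | 50 | **2.0** |
| Platelets, recovery | 75,000 | 75 | 75 | 1.0 |
| Neutrophils, Grade 3 | 1,000 | 1 | 1 | 1.0 |
| Neutrophils, Grade 4 | 500 | 0.5 | 1 | **2.0** |
| Neutrophils, recovery | 1,500 | 1.5 | 1.5 | 1.0 |

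Four of the six pairs reproduce. The two that fail are the Grade 4 pairs. Each is out by exactly two, and each bracket equals the Grade 3 bracket of the same toxicity.

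**Step 2. Follow a count in each disputed band through both rows.**

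| Example | Under the Grade 3 row | Under the Grade 4 bracket |
|---|---|---|
| Platelets 40,000 | No modification of either drug | Ibrutinib interrupted (by the paragraph under the table; the cell itself starts at the restart rule); stopping pembrolizumab is a matter of judgment |
| Neutrophils 700, no fever or infection | Pembrolizumab held; ibrutinib not held | Ibrutinib held; no pembrolizumab hold written |

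In the neutrophil example, the drug with a written hold changes from one row to the other.

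**Step 3. Compare the pembrolizumab entries.**

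| Element | Grade 3 neutropenia | Grade 4 neutropenia | Non-haematological Grade 3 or 4 |
|---|---|---|---|
| Hold | Written | Not written | Written |
| Timed resume-or-discontinue rule | Written | Not written | Written |
| Discretion over discontinuation | Not written | Written | Written, for Grade 4 |

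The third column shows that a hold and the discretion sentence can stand together. Neither the ibrutinib-only paragraph nor the immune-related table supplies a hold for Grade 4 neutropenia.

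**Step 4. Read the Grade 3 entry for one patient.** Take neutropenia that falls to Grade 2 by day 7 and stays there. By the opening sentence the hold continues, because Grade 1 or baseline has not been reached. By the 7-day clause pembrolizumab resumes at the next scheduled dose. The same pair of sentences appears in the non-haematological Grade 3 or 4 row.

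**The case against.** **The brackets look like a copying slip.** Taken literally, they make the Grade 3 and Grade 4 limits identical and leave Grade 3 empty, so a careful reader would doubt them. Section 8.2.1 sets CTCAE 5.0 as the grading system, and section 8.4.1 has the treating physician assign the CTCAE grade. This stands as a reason why misclassification is less likely in practice. It does not remove the mismatch from a table that clinicians act on.

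**The Grade 4 sentence does not forbid a hold.** It concerns discontinuation. The Grade 3 condition, neutrophils below 1,000, has no lower limit, so a count below 500 also meets it numerically. This stands too. A reader might infer that the table contradicts itself on holding pembrolizumab at Grade 4; the text supports only a gap with inverted stringency.

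**The 7/14-day rule may be the timed detail of the hold.** That is a possible reading of the Grade 3 entry, and it makes this the weakest of the three parts. The text does not say so, and asking for clarity is reasonable.

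**The rows do not all interrupt both drugs.** A reader might infer that they do. Grade 3 thrombocytopenia modifies neither drug, Grade 3 neutropenia holds ibrutinib only with infection or fever, and neither haematological Grade 4 row writes a pembrolizumab hold.

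**The number affected is unknown.** Section 2.3.1 gives Grade 3 or 4 neutropenia in 24% and thrombocytopenia in 8% on single-agent ibrutinib. A reader might multiply by 25 (0.24 × 25 = 6; 0.08 × 25 = 2) and conclude that 6 and 2 patients would face conflicting instructions. The documents do not support that. The rates pool Grades 3 and 4 and come from ibrutinib alone. The disputed bands are only part of that range, no split by grade is given, and the rows exclude cytopenia due to marrow involvement.

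**Conclusion.** The point holds in three parts of unequal strength.

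1. **Thresholds.** Two of the six printed pairs, both at Grade 4, are internally inconsistent by a factor of 2.0. This is arithmetic and rests only on the unit readings stated above. The disputed bands are platelets of 25,000 to 50,000/mm³ and neutrophils of 500 to 1,000/mm³.
2. **Pembrolizumab at Grade 4 neutropenia.** No hold is written, although one is written for Grade 3 neutropenia and for non-haematological Grade 3 or 4 events. The omission may be unintended; the documents do not settle it.
3. **Resumption at Grade 3.** The entry is unclear for a patient who improves to Grade 2 but no further.

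The number of patients who would meet these ambiguities cannot be derived from the documents. The 6 and 2 above describe only pooled Grade 3 or 4 incidence on single-agent ibrutinib, scaled to 25 patients.

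A reader might also suppose that the primary analysis is compromised. It is not: the two-stage rule in section 10.2.1 (16 patients, then 25 in total), with its stated power and type I error, does not use these thresholds. The matter is consistency of treatment and safety, and the table should be corrected.

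**What to change.** The sponsor's clinical team should correct the table in section 6.1.8 so that:

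- in the Grade 4 thrombocytopenia and Grade 4 neutropenia rows, the count and the bracket state the same threshold;
- the pembrolizumab entries for Grade 3 and Grade 4 neutropenia are reconciled with each other, saying explicitly whether the absence of a hold at Grade 4 is intended;
- the Grade 3 neutropenia entry says unambiguously how the opening hold and the 7/14-day clause fit together, with the matching wording in the non-haematological row checked at the same time.

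Which threshold and which rule should stand is for the clinical team to decide; none is proposed here. The cost is a table correction by protocol amendment, with the IRB approval that section 13.2 requires. Sample size, endpoints and the statistical analysis do not change.
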